5.6 Withdrawal Criteria

Subjects may withdraw from the study at any time on their own request, or subjects may be withdrawn at any time at the discretion of the investigator or Reistone Biopharma for behavioral or administrative reasons.

If a subject develops a serious infection during the study, defined as any infection (viral, bacterial, and fungal) requiring hospitalization or parenteral antimicrobials, he/she must be discontinued from the study.

All abnormal laboratory events of clinical significance should be followed until the laboratory values have returned to normal or baseline levels. In addition, any subject with a confirmed increase in serum creatinine at the end of study or at discontinuation of at least 0.2 mg/dL and at least 10% above the average of screening and baseline value will be followed up with retesting every one to two weeks until the creatinine elevation has fully reversed to within 10% of the subject's baseline value or has been stable.

If a subject has any clinically significant, study-related abnormalities at the conclusion of the study, the medical monitor (or designated representative) should be notified, and every effort should be made to arrange follow-up evaluations at appropriate intervals to document the course of the abnormalities

The reason for a subject discontinuing from the study will be recorded in the eCRF. A discontinuation occurs when a randomized subject ceases participation in the study, regardless of the circumstances, prior to completion of the protocol. The investigator must determine the primary reason for discontinuation. Withdrawal due to adverse events should be distinguished from withdrawal due to insufficient response according to the definition of adverse event noted in Section 7.3.10. The final evaluation required by the protocol will be performed at the time of the study discontinuation. The investigator will record the reason for study discontinuation, provide or arrange for appropriate follow-up if required.

5.7 Pre-Screen and Screen Failure

Subjects will be assigned a subject number after they have signed a written informed consent and completed at least one additional study procedure (study procedures do not include washout of any medication).

Screen failure is defined as any subject who has been assigned a subject number but does not continue in the study beyond Visit 1 (Screening) or any subject who completes Visit 1 and enters the run-in period but is subsequently found to be ineligible for the study-based procedures (e.g., laboratory, ECG, or Endoscopy) conducted at Visit 1. The study interactive voice response system (IVRS) used to track study enrolment, will be contacted to report screen failures.

Additionally, the following information will be collected in the eCRF for screen failures:

• Screening Visit Date

- Subject Number
- Demographic information, including race, age, and gender
- Inclusion/Exclusion Criteria
- Reasons for screening failure
- Primary method of subject recruitment
- Serious adverse event (SAE) information

In most circumstances, subjects who failed screening could not be re-screened. In rare instance, subjects may be eligible for re-screening. However, the re-screening of subjects must be approved by the study medical monitor prior to re-screening.

5.8 Early Withdrawal

The definition of an early withdrawal from the study will be any subject who is randomized to double-blind medication and, for any reason, is withdrawn prior to completion of the Visit 6 procedure (Week 12).

Subjects may voluntarily discontinue participation in the study at any time. The investigator may also, at his/her discretion; discontinue the subject from participating in the study at any time. In addition, the investigator must make every effort to have the subject return to the clinic as soon as possible after discontinuation of study drug for an Early Withdrawal Visit. An Early Withdrawal Visit may occur at a regular scheduled clinic visit or between clinic visits. The following evaluations and procedures should be completed and recorded in the eCRF

- Concomitant Medication Assessment
- AE/SAE assessment
- Physical examination (documented in original document only)
- Vital signs
- Collect and review patient questionnaires (pruritus NRS, DLQI)
- Collect used study medication (blinded study medication)
- Topical triamcinolone used was collected and weighed
- Assess compliance with study medication
- 12-lead ECG
- Laboratory evaluations (including biochemistry, hematology, pregnancy test for female subjects of childbearing potential and routine urinalysis)
- Call IVRS to report the subject's early withdrawal from the study
- Investigator's Global Score (IGA)
- Eczema Area and Severity Index (EASI)
- Scoring atopic dermatitis (SCORAD)

Subjects who withdraw from the study after randomization to treatment cannot be re-screened and will not be replaced. If a subject withdraws from the study, and withdraws consent for further disclosure, no further assessments will be performed and no additional data will be collected. The sponsor may retain and continue to use any data collected prior to such withdrawal of consent.

Thyroid specific criteria:

Subjects with deranged TSH level (outside of normal range) only, but normal free T4 or free T3. Investigator can follow-up the subject with thyroid function test and assess clinically in 4 weeks.

Deranged TSH level, with associated deranged free T4 and/or free T3(outside of normal range), the investigator should assess subject's clinical condition and decide if the subject should be withdrawn.

Subject with signs and/or symptoms suggestive of hypothyroidism or hyperthyroidism should have laboratory thyroid function performed. If any of the thyroid parameters (TSH, free T4, or free T3) were outside of normal range, the subject is to be withdrawn.

5.9 Stopping Criteria

The stopping safety criteria are as follows:

- Liver chemistry threshold stopping criteria have been designed to assure subject safety and to evaluate liver event etiology (in alignment with the FDA premarketing clinical liver safety guidance). Study treatment will be stopped if the liver chemistry stopping criteria is met. Refer to Section 7.3.8 Liver Chemistry Stopping and Follow-up Criteria.
- Subject that meets the QTc criteria below will be withdrawn from the study. The QT correction formula used to determine discontinuation should be the same one used throughout the study.
 - QTc, QTcB/QTcF > 500ms
 - Change from baseline: QTc > 60ms

Withdrawal decisions are to be based on an average QTc value of triplicate ECGs. If an ECG demonstrates a prolonged QT interval, obtain 2 more ECGs over a brief period, and then use the averaged QTc values of the 3 ECGs to determine whether the subject should be discontinued from the study.

- An unacceptable adverse event, as determined by the Investigator and the medical monitor
- Any unacceptable adverse event that is thought to be related to the investigational product may result in the study being terminated
- Significant protocol deviation. The discovery that post-randomization the subject failed to meet protocol entry criteria or did not adhere to protocol requirements, and continued participation poses an unacceptable risk to the subject's health
- If the subject is found to be pregnant, the subject should be withdrawn immediately. The procedure is detailed in Section 7.3.10

5.10 Premature Study Termination

The sponsor may discontinue the study if the study becomes unjustifiable for medical ethical reasons, for poor enrollment, or because of discontinuation of clinical development of the investigational product.

The clinical study may be terminated prematurely or suspended at the request of health authorities or if new safety or efficacy information leads to an unfavorable risk benefit judgment for the investigational product.

If a study is prematurely terminated or discontinued, Reistone will promptly notify the investigator. After notification, the investigator must contact all participating subjects and the hospital pharmacy (if applicable) within 7 days. As directed by Reistone, all study materials must be collected and all eCRFs completed to the greatest extent possible.

5.11 Time and Event Tables

See details in Table 1.

Table 1. Time and Event Table

Period	Screening	Baseline	Treatment period			Follow-up/ EW ¹²	
Visit	1	2	3	4	5	6	7
Study Week	-4 to -1	0	1	4	8	12	14
Study Day	-28to -1	0	7 ± 2 days	28 ± 3 days	56 ± 3 days	84 ± 3 days	98 ± 3 days
Procedures		•					
Written Informed Consent ¹	X						
Demography/Medical History ²	X						
Physical Examination	X	X	X	X	X	X	X
Height	X						
Weight	X						X
Chest X-ray ³	X						
Inclusion/Exclusion Criteria	X						
Randomization criteria		X					
Study Drug Dispensing		X		X	X		
Study Drug Accountability				X	X	X	x 13
Enrollment Visit in IVRS ⁴	X	X	X	X	X	X	x 13
Assessment of effectiveness							
Investigator's Global Assessment (IGA)	X	X	X	X	X	X	x ¹³
Eczema Area and Severity Index (EASI)	X	Х	X	X	X	X	x ¹³
Scoring Atopic Dermatitis (SCORAD)	X	X	X	X	X	X	x ¹³
Pruritus numeric rating scale (NRS)	X	X	X	X	X	X	x ¹³
Dermatology quality of life index (DLQI)	X	X	X	X	X	X	x ¹³
Photography ⁵	X	X	X	X	X	X	x ¹³
safety assessment							
12-lead ECG	X	X	X	X	X	X	X

Vital signs (blood pressure, heart rate, temperature and respiratory rate) ⁶	X	х	X	X	X	X	Х
Adverse Event Assessment ⁷		X	X	X	X	X	X
Laboratory Evaluation							
Hematological and biochemical tests	X	X	X	X	X	X	х
Urinalysis	X	X	X	X	X	X	X
Lipid Profile (fasting)		X	X	X	X	X	X
TSH, fT3, fT4	X	X	X	X	X	X	X
QuantiFERON-TB Gold or T-SPOT.TB test	X						
Hepatitis B surface antigen, Hep C Ab, HIV test	X						
Immunoglobulin E (IgE)	X	X	X	X	X	X	x ¹³
Urine Pregnancy Test 8		X	X	X	X	X	X
β-HCG (blood) ⁹	X						
Medication							
Concomitant Medication Assessment	X	X	X	X	X	X	Х

- 1. Written informed consent must be obtained prior to performing any Visit 1 procedures or initiating any alterations in a subject's medications.
- 2. Atopic Dermatitis Disease History includes collection of details of AD: AD diagnosis, the use of topical treatments, systemic treatments and other treatments for AD.
- 3. Only to be performed if there is no chest X-ray or CT scan available within 3 months of Visit 1.
- 4. IVRS is a randomization system used to record all patient visits.
- 5. Subjects will be photographed at a distance of 1m by a fixed investigator at each visit (the principle of photography is to reflect the characteristics of AD skin lesion to the greatest extent). When photographed, face and private part will be well covered.
- 6. Vital signs include resting blood pressure, heart rate, body temperature and respiratory rate. It is advised to measure them before any procedures or questionnaires.
- 7. Adverse events and serious adverse events will be collected from the start of study drug treatment (Visit 2) to the telephone follow-up period. However, any serious adverse events will be recorded from the time of consent.
- 8. Urine pregnancy test to be done in females of childbearing potential only at scheduled visit
- 9. β -Human Chorionic Gonadotrophin(β-HCG) to be done in females of childbearing potential at screening visit, and only to be done if urine pregnancy test positive at other study visits.

- 12. The early withdrawal visit should be done 2 weeks after the last dose/decision of withdrawal.13. Only to be conducted in the early withdrawal subjects.

6. Study Treatments

6.1 Investigational product/placebo supply

SHR0302 tablets and matching placebo tablets will be dispensed for subjects to take orally during the treatment period. During the treatment period, subjects will be randomized in a ratio of 1: 1: 1 to 4 mg QD, 8 mg QD, or placebo.

SHR0302 will be provided as combination of 4 mg tablets, including the matching placebo by the sponsor. At study visit on Day 0, Week 4 and Week 8, sufficient trial medication will be dispensed to complete dosing for 4 weeks.

At the Week 12 visit or follow-up visit (if the patient withdraws), the subject must return all trial medication and the amount of medication returned will be recorded.

6.1.1 Study Drug Dispensing

Investigational product will be assigned to subjects at the baseline visit once successfully randomized through the tele-randomization system. The investigator or appropriate delegate at the site will access the tele-randomization system (IVRS) at baseline visit to receive correct container numbers to be dispensed to the subject. All medication dispensed or returned will be documented in the eCRF.

After completion of the 12-week treatment period, all subjects will be followed for an additional 2 weeks.

6.1.2 Study Drug Administration

Study drug will be self-administered by the subject once daily orally in the morning.

However, the first dose will be administered at the clinic at baseline (Day 0). Subjects should take their oral dose at the clinic at the Week 4, Week 8, and Week 12 visits. Study drug may be taken with or without food.

6.2 Treatment Assignment

Subjects who meet all inclusion criteria and do not meet any of the exclusion criteria will be randomized in a 1: 1: 1 allocation ratio to SHR0302 4 mg QD, SHR0302 8 mg QD, or placebo during the treatment period.

6.3 Blinding

Investigational product taken during the 12-week treatment period will remain double-blind. Neither the subject nor the study physician will know which study medication the subject is receiving.

In order to preserve blinding and ensure patients compliance throughout the study, the study drug packaging has been designed with detailed consideration. All the arms are administered under

oncedaily (QD) dosing regime and placebo is used according to the schedule in the table below. (Table 2)

Table 2. Study drug package design for treatment group

Study Group	Dose (QD)
	Day 0 to Day 84
4mg SHR0302	4mg tablet + placebo tablet
8mg SHR0302	4mg tablet + 4mg tablet
placebo	Placebo tablet + placebo tablet

At each dosing time (morning), subjects will take two tablets.

The investigator or treating physician may unblind a subject's treatment assignment **only in the case of an emergency**, when knowledge of the study treatment is essential for the appropriate clinical management or welfare of the subject. Whenever possible, the investigator must first discuss options with the Reistone Biopharma/designated CRO Medical Monitor or appropriate Reistone Biopharma/designated CRO study personnel before unblinding the subject's treatment assignment. If this is impractical, the investigator must notify Reistone Biopharma/designated CRO as soon as possible, but without revealing the treatment assignment of the unblinded subject, unless that information is important for the safety of subjects currently in the study. The date and reason for the unblinding must be recorded in the appropriate data eCRF.

Reistone Biopharma/designated CRO staff may unblind the treatment assignment for any subject with an SAE. If the SAE requires that an expedited regulatory report be sent to one or more regulatory agencies, a copy of the report, identifying the subject's treatment assignment, may be sent to clinical investigators in accordance with local regulations. Subjects will be withdrawn if the treatment code becomes unblinded. The primary reason for discontinuation (the event or condition which led to the unblinding) will be recorded in the eCRF.

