7.4 Pharmacokinetics

Blood samples for pharmacokinetics exposure-response analysis of SHR0302 will be collected from randomized subjects at the following time points (Table 7). If not, please address the reason.

On the days of PK sampling at Weeks 8 and 12, subjects will take their dose of study medication for that day at the study site.

Blood samples will be analyzed using validated analytical methods. Only samples from subjects who have received active drug (i.e., SHR0302) will be measured for the analysis (SHR0302). Contracted PK analysis laboratory personals will be unblinded for the analysis purpose. Samples from subjects receiving placebo will not be analyzed.

8. Data Management (DM)

For this study subject data will be entered into Reistone Biopharma/designated CRO defined electronic case report forms (eCRFs), transmitted electronically to Reistone Biopharma /Designated CRO and combined with data provided from other sources in a validated data system. Management of clinical data will be performed in accordance with applicable Reistone Biopharma/designated CRO data review, verification and cleaning procedures to ensure the integrity of the data, e.g., removing errors and inconsistencies in the data. Adverse events and concomitant medications terms will be coded using MedDRA. An appropriate medical dictionary that covers all approved drugs in the region will be referenced. eCRFs (including queries and audit trails) will be retained by Reistone Biopharma/designated CRO, and copies will be sent to the investigator to maintain as the investigator copy. In all cases, subject initials will not be collected or transmitted to Reistone Biopharma/designated CRO.

9. Data Analysis and Statistical Considerations

Detailed summary and statistical analysis of the data collected in this study will be recorded in the Statistical Analysis Plan (SAP) and maintained by Reistione Biopharma/Designated CRO. The document may provide a revision of the plan in the protocol; however, any major revision of the definition of the primary endpoint and/or its analytical approach should be reflected in the protocol amendments.

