9.2.1 Analysis of the primary efficacy endpoint

For the primary endpoint, the method of normal approximation will be used to test whether each drug group is superior to the placebo group. Subjects who early withdraw from the study for any reason will be considered as non-responders.

Other analyses for the primary endpoint will be described in the statistical analysis plan (SAP).

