10.7 Independent Data Monitoring Committee (IDMC)

A data monitoring committee for efficacy is not required for this study. Data safety monitoring will be continuously conducted by the Sponsor study team. or Reistone Biopharma /designated CRO will hold regular data monitoring meetings to review the data in order to ensure data accuracy and protocol compliance. Safety data will also be continuously reviewed to detect early signals and identify risk.

10.8 Provision of study results to Investigators, posting to the Clinical Trial Registry and Publication

Where required by applicable regulatory requirements, an investigator signatory will be identified for the approval of the clinical study report. The investigator will be provided reasonable access to statistical tables, figures, and relevant reports and will have the opportunity to review the complete study results at a Reistone/designated CRO site or other mutually agreeable location.

Reistone/designated CRO will also provide the investigator with the full summary of the study results. The investigator is encouraged to share the summary results with the study subjects, as appropriate. Reistone/designated CRO will provide the investigator with the randomization codes for their site only after completion of the full statistical analysis. The results summary will be posted to the Clinical Study Register when appropriate determined by Reistone.

In addition, a manuscript will be submitted to a peer-reviewed journal for publication. The results summary will be posted to the Clinical Study Register if required by legal agreement, local law or regulation.

11.Reference

- 3. Hen Gu JZ. Guidelines for the diagnosis and treatment of atopic dermatitis in China. *Chin J Dermatol.* 2014;47(7):4.

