14.2 PRIMARY EFFICACY ANALYSIS

Analysis of the primary efficacy endpoint will be based on FAS.

The primary efficacy endpoint for this study is the percentage of subjects achieving IGA response at Week 12. IGA is the investigator's global assessment of the subject's general condition and consists of a 6-point severity scale from clear to very severe disease ("complete clearance", "almost

complete clearance", "mild", "moderate", "severe", and "very severe"). IGA response is defined as IGA score of 0/1 (complete or almost complete clearance of skin lesions) with an improvement in IGA score by ≥ 2 from baseline.

Subjects who early withdraw from the study for any reason will be considered as non-responders at each post-withdrawal assessment time point. Descriptive summaries of the primary efficacy endpoint will be based on non-missing data only.

Due to the impact of the COVID-2019 pandemic, subjects may have their primary efficacy endpoint assessed outside the scheduled time window of visit 6. If the primary efficacy endpoint is missing within the planned time window (between study days 82 and 88), it will be considered to impute with results of assessment within 89 to 102 study day (ie, extended visit).

The method of normal approximation to binomial will be used to test whether each active drug group is superior to the placebo group. Estimation of the difference and its 90% confidence interval between each drug group and the placebo group, as well as the corresponding p value for test will be provided.

Referenced SAS code:

```
PROC FREQ DATA = adam.adeff;  
  TABLE treat*aval/CHISQ RISKDIFF (CL = WALD) ALPHA = 0.1;  
  RUN;
```

In the above codes, variables are defined as follows:

Aval = IGA response at Week12

Treat = treatment group

In addition, IGA response and its 90% confidence interval at Week 12 will also be provided for each treatment group.

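### Sponsor or CRO staff may break the code for any SAE, and the withdrawal sentence that follows can then turn that code break into a primary non-response

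*Protocol*

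**What the plan says.** Protocol 6.3 treats the two sides differently. The investigator may break a code only in an emergency. If the sponsor could not be consulted first, it is told afterwards without the assignment, unless the safety of other subjects requires it. For the sponsor side the rule is: "Reistone Biopharma/designated CRO staff may unblind the treatment assignment for any subject with an SAE". No condition on causality, expectedness or reporting duty is attached, and no group of staff is named. For expedited cases, a report identifying the arm "may be sent to clinical investigators in accordance with local regulations". The paragraph then states: "Subjects will be withdrawn if the treatment code becomes unblinded". The triggering event is to be recorded as the reason for discontinuation.

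Protocol 5.8 defines early withdrawal as withdrawal, for any reason, before the Week 12 (Visit 6) procedures are complete. Protocol 9.2.1 then says: "Subjects who early withdraw from the study for any reason will be considered as non-responders". SAP 14.2 agrees: "Subjects who early withdraw from the study for any reason will be considered as non-responders at each post-withdrawal assessment time point".

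On who sees what, Protocol 10.7 says: "Data safety monitoring will be continuously conducted by the Sponsor study team". SAP 4.3 describes emergency unblinding by the investigator or attending doctor and one release of all codes after database lock. It does not mention sponsor unblinding for SAEs, and SAP Table 2, which lists differences from the protocol, does not either. SAP 7 and 13.2 have PPS and ESS exclusions and major deviations settled at data review before unblinding.

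**The concern.** Two rules that are each ordinary combine badly. A broad permission to look up a code, followed by a withdrawal rule with no stated scope, lets an act of sponsor safety handling fix a subject's Week 12 outcome. A subject whose SAE has resolved, and who might have stayed and responded, becomes a non-responder because someone looked up the code. The trigger is wide: the SAE definition in Protocol 7.3.12 includes any hospitalization and resolves doubt about hospitalization towards serious.

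The second issue is exposure of codes. The protocol already defines a narrower class of events, SUSARs, in 7.3.11, and keeps pregnancies blinded to the study team in 7.3.9. It gives SAEs no comparable protection. Staff who know individual codes could be the same people who review safety data or judge deviations and supportive-set exclusions.

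**Working it through.** **The chain, link by link**

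1. An SAE occurs. Sponsor or CRO staff may unblind (Protocol 6.3).
2. The code has become unblinded, so the subject is withdrawn (same paragraph; no exception for who broke the code).
3. If this happens before Visit 6 is complete, it is early withdrawal (Protocol 5.8).
4. Early withdrawal for any reason is non-response at Week 12 (Protocol 9.2.1, SAP 14.2).

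No other section interrupts this chain. A code broken after Visit 6 is complete leaves the primary outcome unchanged.

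**Inputs for the size (SAP 6, 8 and 14.1)**

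- 35 subjects per arm; response 26%, 26% and 6%; two-sided 0.10 with Hochberg over two comparisons; stated power about 82% for at least one dose.
- The decision figure is not shown in the text, so the standard rule is used: reject both if the larger p ≤ 0.10; otherwise reject the smaller if p ≤ 0.05.
- Assumption: a fraction f of subjects is unblinded and withdrawn before Week 12. No SAE or unblinding rate is given.

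**Reproducing the stated power**

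Three independent binomials were enumerated exactly, with the pooled two-proportion test and the Hochberg rule, counting a win when at least one dose is significant in the right direction. Result: 82.7%, against 82% stated. The protocol's own design (40 completers per arm, 30% against 10%) gives 80.8%, against 81% stated. With unpooled variance the results are 84.5% and 81.3%.

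**Effect on power**

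If those withdrawn would have responded at their arm's rate, the rate becomes p(1 − f). For example, at f = 3% an active arm has 0.26 × 0.97 = 0.2522.

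| f (assumed) | Active arms only | All arms equally |
|---|---|---|
| 0 | 82.7% | 82.7% |
| 1% | 82.0% | 82.3% |
| 2% | 81.3% | 81.9% |
| 3% | 80.5% | 81.5% |
| 5% | 78.9% | 80.7% |

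Expected responders lost across both active arms: 70 × 0.01 × 0.26 = 0.18 at 1%, and 70 × 0.03 × 0.26 = 0.55 at 3%.

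**Effect on one comparison**

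z = (x₁ − x₂)/35 ÷ √[p̄(1 − p̄) × 2/35], with p̄ = (x₁ + x₂)/70. The design rates give 0.26 × 35 = 9.1 and 0.06 × 35 = 2.1, so about 9 against 2.

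| Active vs placebo responders | p̄ | z | p |
|---|---|---|---|
| 9 vs 2 | 0.157 | 2.30 | 0.022 |
| 8 vs 2 | 0.143 | 2.05 | 0.040 |
| 7 vs 2 | 0.129 | 1.79 | 0.074 |
| 6 vs 2 | 0.114 | 1.50 | 0.133 |

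At the design rates one lost responder takes p from 0.022 to 0.040, still below both Hochberg thresholds. Two losses in one arm give 0.074, past the 0.05 step but not past 0.10. A single loss reverses the conclusion only in borderline data. If both doses stand at 7 vs 2, both p-values are 0.074 and both are rejected. After one loss the larger p is 0.133 (> 0.10) and the smaller is 0.074 (> 0.05), so neither is rejected.

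**The case against.** The strongest reply is that little of this is likely to happen, and that much of it is inferred from silence.

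- **An SAE must come first, and unblinding is permissive.** One might infer that sponsor handling alone can convert a subject. It cannot. Some subjects with SAEs would leave anyway, for example with a serious infection (Protocol 5.6), so the added loss is smaller than the SAE count. This stands and limits the size.
- **The PK laboratory.** Because the withdrawal sentence names no recipient, a reader might infer that it also catches the planned step "Contracted PK analysis laboratory personals will be unblinded for the analysis purpose". The context does not support this. The sentence closes a discussion of code breaks for individual subjects, and the literal reading would withdraw subjects for routine sampling.
- **Analysis sets.** A reader might infer that the main analysis set could be shaped with codes in hand. SAP 7 rules that out: the FAS is everyone randomized and dosed, with no discretionary exclusion. Early codes could touch only the supportive PPS and ESS and the deviation decisions. No document says that the code-breakers also decide exclusions, and a separate safety plan could hold a safeguard that is not visible here.
- **Investigators.** Arm-naming reports are confined to expedited cases. The subject concerned is withdrawn, so a later rating cannot make that subject a Week 12 responder. Influence on the rating of other subjects is possible but not shown.

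What remains is the explicit rule itself: an unrestricted sponsor permission, an unscoped withdrawal sentence, and an SAP that does not acknowledge the route.

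**Conclusion.** The point holds as a gap in blinding and in the handling of early withdrawal, not as a power error. After an SAE, a discretionary code break before Visit 6 is complete can determine the primary outcome, and the documents do not say who may see codes or keep those people apart from data review. At an assumed 1% to 3% of active-arm subjects affected, power falls by about 0.7 to 2.2 points from 82.7%. These figures rest on the SAP design of 35 per arm and on affected subjects responding at their arm's rate. The inference that one lost responder would generally cost a significant result is not supported: it does so only near the thresholds. The gap is worth closing because it arises from stated text and is cheap to correct.

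**What to change.** In Protocol 6.3:

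- Restrict sponsor and CRO code breaks to SAEs that need an expedited report.
- Have them made by existing safety staff with no role in data review, analysis-set decisions or site contact.
- Send sites blinded copies of the report where local regulations allow.
- Log every code break.

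Reconcile the withdrawal sentence in 6.3 with sponsor-side unblinding and with SAP 4.3, which should describe the route. Which withdrawal rule applies is for the sponsor's clinical team to decide. Emergency unblinding by sites is untouched.

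The cost is protocol and SAP wording plus a role assignment, with no added subjects, visits or data. The downside is that the study team loses direct access to SAE codes.
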